8.10.1.2. Select Echocardiogram Cardiac Parameters

Descriptive statistics for Echocardiogram cardiac parameter (see Section 2.3.4.1.2) results, change from baseline, and percent change from baseline will be presented by visit for each treatment group. Change from baseline and percentage change from baseline will be analyzed using an ANCOVA model including fixed effects for randomization strata and treatment group, with the baseline value included as a covariate.

LVEF is captured in the eCRF as text to allow entry of ranges that may be recorded on the source document report. If the eCRF LVEF value contains only numbers, “%”, or “>” the numeric portion of the value will be used for LVEF summary. If the eCRF value contains a range, the midpoint of the range will be used as the value for LVEF summary.

The number and percentage of subjects with LVEF (%) change from baseline categorized as follows will be summarized: >20% Reduction, 10-20% Reduction, <10% Increase - <10% Reduction, 10-20% Increase, and >20% Increase. The number and percentage of subjects with LPWd (mm) change from baseline categorized as follows will be summarized: ≥ 2 mm Increase and < 2 mm Increase.

8.10.2. Functional Endpoint Analyses

8.10.2.1. 6MWT Distance

In addition to the key secondary endpoint, 6MWT distance, change from baseline, and percent change from baseline to all visits will be analyzed in the same manner described in Section 8.8.2.

The 6MWT change from baseline will also be categorized as follows:

- ≥ 30 -meter decline (Worsening)
- < 30-meter decline to < 30-meter improvement (No Change)
- ≥ 30 -meter improvement (Improvement).

The categorical change from baseline will be summarized by visit for each scheduled post-baseline visit. For each post-baseline visit ordinal logistic regression will be performed with 6MWT categorical change from baseline (Worsening, No Change, Improvement) as the dependent variable and factors for treatment group and randomization strata. Estimates of the proportional odds ratio comparing NEOD001 to placebo and the 95% CI of the odds ratio will be presented. An odds ratio greater than 1 favors the NEOD001 treatment group.

8.10.3. Quality of Life Endpoint Analyses

8.10.3.1. SF-36v2

In addition to the key secondary endpoint, the SF-36v2 PCS and MCS scores and the eight subscales to all visits will be analyzed in the same manner described in Section 8.8.1. The cumulative distribution of change from baseline at the Month 9 visit will also be plotted.

The rate of change (i.e. slopes) in the SF-36v2 PCS and MCS scores and the eight subscales will be analyzed in the same manner described in Section 8.8.3.

Table 5 below presents the responder definitions recommended by Optum for SF-36v2 domains and component summary scores.

Table 5: Responder Criteria for SF-36v2 Domains and Summary Measures

SF-36v2 Domain	Responder Threshold (\geq)
Physical Functioning (PF)	4.3
Role-Physical (RP)	3.4
Bodily Pain (BP)	6.2
General Health Perceptions (GH)	7.2
Vitality (VT)	6.2
Social Functioning (SF)	6.9
Role-Emotional (RE)	4.5
Mental Health (MH)	6.2
Physical Component Summary (PCS)	3.4
Mental Component Summary (MCS)	4.6

Response will be defined as greater than or equal to the specified threshold and non-response will be less than the specified threshold. Response will be derived for each subject at each visit for each subscale, MCS score, and PCS score. NEOD001 and placebo will be compared on each response distribution at each visit using a CMH test stratified by the randomization stratification factors. The number and percentage, with associated two-sided 95% CIs, of subjects in each category of response (response, nonresponse) at each visit will be presented by treatment group.

8.10.3.2. KCCQ

All KCCQ subscores and overall summary score, changes and percent changes from baseline to all visits will be analyzed in the same manner described in Section 8.8.1.

The rate of change (i.e. slopes) in the KCCQ subscores and overall summary score will be analyzed in the same manner described in Section 8.8.3.

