2.3.4.3.2. KCCQ

The KCCQ is a self-administered, 15-item questionnaire to assess physical limitation, symptom stability, symptom frequency, symptom burden, total symptom score, self-efficacy, quality of life, social limitation, overall summary score, and clinical summary score ([Appendix 8](#)). Scores are transformed to a range of 0-100, in which higher scores reflect better health status. The change and percent change from baseline to each visit in the KCCQ subscores and overall summary score will be evaluated.

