APPENDIX 8. KANSAS CITY CARDIOMYOPATHY QUESTIONNAIRE (KCCQ)

The KC Cardiomyopathy Questionnaire

The following questions refer to your **heart failure** and how it may affect your life. Please read and complete the following questions. There are no right or wrong answers. Please mark the answer that best applies to you.

1. **Heart failure** affects different people in different ways. Some feel shortness of breath while others feel fatigue. Please indicate how much you are limited by **heart failure** (shortness of breath or fatigue) in your ability to do the following activities over the past 2 weeks.

Place an X in one box on each line

Activity	Extremely Limited	Quite a bit Limited	Moderately Limited	Slightly Limited	Not at all Limited	Limited for other reasons or did not do the activity
Dressing yourself						
Showering/Bathing						
Walking 1 block on level ground						
Doing yardwork, housework or carrying groceries						
Climbing a flight of stairs without stopping						
Hurrying or jogging (as if to catch a bus)						

2. Compared with 2 weeks ago, have your symptoms of **heart failure** (shortness of breath, fatigue, or ankle swelling) changed?

My symptoms of **heart failure** have become...

Much worse	Slightly worse	Not changed	Slightly better	Much better	I've had no symptoms over the last 2 weeks
					

3. Over the past 2 weeks, how many times did you have **swelling** in your feet, ankles or legs when you woke up in the morning?

- | | | | | |

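### KCCQ symptom stability already records a 2-week change, so its planned slope, percent change and within-arm change from baseline do not measure symptom benefit and can take the wrong sign

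*SAP*

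**What the plan says.** SAP 2.3.4.3.2 describes the KCCQ as a questionnaire "to assess physical limitation, symptom stability, symptom frequency, symptom burden, total symptom score, self-efficacy" and further domains. It says of all of them: "Scores are transformed to a range of 0-100, in which higher scores reflect better health status". The endpoint is then set without exception: "The change and percent change from baseline to each visit in the KCCQ subscores and overall summary score will be evaluated". Protocol 3.2.4 lists the same exploratory endpoint.

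SAP 8.10.3.2 gives the analysis. First, "All KCCQ subscores and overall summary score, changes and percent changes from baseline to all visits will be analyzed in the same manner" as section 8.8.1, which is the MMRM on change from baseline with baseline as a covariate. Second, "The rate of change (i.e. slopes) in the KCCQ subscores and overall summary score will be analyzed in the same manner" as section 8.8.3, which is the random-slope model with time in months and baseline included among the time points. SAP section 10 lists no exception for symptom stability.

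Question 2 of the instrument (SAP Appendix 8; Protocol Appendix 10) begins "Compared with 2 weeks ago, have your symptoms of" heart failure changed. It offers five answers from much worse to much better, and a sixth for subjects who had no symptoms. No other item asks about change. Neither document prints the scoring key, so the link from question 2 to symptom stability is inferred from the wording.

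**The concern.** Most KCCQ items describe the subject's state over the last 2 weeks, and for those a change from baseline or a slope has its usual meaning. Question 2 describes direction instead. A severely limited but stable subject and a well, stable subject both answer *not changed*. A subject who improves and holds the gain answers *better* while it is happening and then returns to *not changed*.

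A straight line through such answers does not trace symptoms over 12 months. An early answer of *better* followed by *not changed* pulls the line down, so a real and lasting gain can be reported as a negative slope on a scale described as higher is better. Change and percent change within an arm depend on what the subject happened to report in the 2 weeks before Screening. At stake is a set of formal estimates, confidence intervals and tests on a heart-failure symptom score that may be read in the wrong direction.

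**Working it through.** The plan states no figure for this point, so there is none to reproduce.

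**Inputs**
- KCCQ schedule: Screening, Months 3, 6, 9 and 12, and the end-of-study visit (SAP Table 1). Target study days are 1, 56, 140, 224, 308 and 338 (SAP Table 4).
- In months from Day 1, (day - 1)/30.4375: t = 0, 1.81, 4.57, 7.33, 10.09, 11.07.
- Baseline: last value before the first infusion (SAP 2.2.7), which for the KCCQ is Screening.
- Assumed, not in the documents: equal steps, with *much worse* 0, *slightly worse* 25, *not changed* 50, *slightly better* 75 and *much better* 100.

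**1. Slope.** The least-squares slope is Σ(t - t̄)y / Σ(t - t̄)², with t̄ = 5.81 and Σ(t - t̄)² = 99.6. If one visit j is raised by s points above an otherwise constant score, the slope is s(t_j - t̄)/99.6. For a baseline of *not changed*, a one-step gain (s = 25) that is then kept, and scores that return to 50:

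| Gain reported at | Calculation | Slope per month | EEOS change |
|---|---|---|---|
| Month 3 | 25 × (-4.00)/99.6 | -1.00 | 0 |
| Month 6 | 25 × (-1.24)/99.6 | -0.31 | 0 |
| between recall windows | no raised answer | 0 | 0 |
| Month 9 | 25 × 1.52/99.6 | +0.38 | 0 |
| Month 12 | 25 × 4.28/99.6 | +1.07 | 0 |
| EEOS | 25 × 5.26/99.6 | +1.32 | +25 |

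If the gain is scored 100 instead of 75, the Month 3 and Month 6 slopes become -2.01 and -0.62. A gradual gain that stops by Month 6 (50, 75, 75, 50, 50, 50) gives -1.32; one that stops by Month 9 gives -0.94. For comparison, a score of current level that rises 25 points by Month 3 and stays there gives a slope of 25 × 5.81/99.6 = +1.46 and an EEOS change of +25.

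The sign for a single raised answer does not depend on the assumed steps. The mean target day is 1067/6, about day 178. Months 3 and 6 lie before it, so a raised answer there gives a negative slope under any increasing coding.

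**2. How often this happens.** The five 14-day recall windows cover 70 of 337 days, about 21%. In a two-arm simulation every active subject makes a one-step kept gain and no placebo subject does (65 per arm, assumed SD 12, complete data, per-subject slopes). The slope difference depends on when gains occur: -1.00 per month for onsets on days 42-56, -0.26 for days 1-56, -0.13 for days 1-140, about 0 for days 1-324 and +0.11 for days 140-308. The EEOS difference is about 0 in all five.

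**3. Change and percent change within an arm.** Take a subject who answers *not changed* (50) at every visit after baseline:
- baseline 25 (*slightly worse*): change +25, percent change +100%
- baseline 50: 0 and 0%
- baseline 75 (*slightly better*): -25 and -33%
- baseline 0 (*much worse*): +50, percent change undefined

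Symptoms on treatment are the same in all four cases.

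**4. The MMRM arm difference.** Write the section 8.8.1 model as Y_j - B = α_j + τ_j·Z + β·B, where Z is treatment and B is baseline. Moving B across gives Y_j = α_j + τ_j·Z + (β + 1)·B. The treatment difference τ_j is the same whether change or the observed score is modelled. The same step is not available for (Y_j - B)/B, because the division by B differs from subject to subject.

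**The case against.** The strongest reply is that randomization and the baseline covariate protect the comparison that matters. As step 4 shows, this is correct for absolute change. A reader might infer that analysing a change of a change biases or reverses the MMRM treatment difference. The documents do not support that, because the planned contrast at each visit is the baseline-adjusted difference in the observed score.

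A reader might also infer that the plan's use of change from baseline hides a lasting benefit at EEOS. It does not. For a gain completed before the last 2 weeks, the observed answers at EEOS are *not changed* in both arms, with or without subtraction. The recall period is a property of the item, and the fix below does not remove it. A benefit reported at Month 3 still appears in the Month 3 contrast, because 8.10.3.2 covers all visits.

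Nor does every maintained improvement give a worsening slope. The table shows negative, zero and positive slopes according to timing, and gains spread over most of follow-up give a slope difference near zero.

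Two further limits stand. The item mapping and coding are inferred. An undefined percent change at baseline 0 could arise with other 0-100 scores and is not peculiar to this one. None of these replies makes the slope, the percent change or the within-arm change of this score interpretable.

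**Conclusion.** The point holds in limited form. For symptom stability, the planned slope, percent-change and within-arm change results do not measure symptom benefit. The slope can have the wrong sign for an early gain that is kept: about -1.0 points per month if reported at Month 3 and -0.3 if at Month 6, under 25-point steps. The arm difference in absolute change from the baseline-adjusted MMRM is not affected by the subtraction and can be read as a difference in recent 2-week change.

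This rests on question 2 being the item behind symptom stability, on an increasing coding for the sign, and on equal 25-point steps for the sizes. The slopes are least-squares values with complete data at target days. The within-subject covariance in section 8.8.3 and missing visits would alter the weights.

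Severity is minor. The KCCQ is exploratory and outside the testing sequence in SAP 8.6, so no primary or key secondary test changes.

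**What to change.** In SAP 2.3.4.3.2 and 8.10.3.2, exclude symptom stability from the change, percent-change and slope analyses. Report the observed response at each visit as worse, not changed or better. Compare arms at each visit with ordinal logistic regression including the randomization strata, or with a van Elteren test stratified by them, and state that the result describes change over the last 2 weeks only. Both methods are already in the SAP (8.10.2.1 for the categorized walk test; 8.8.1 and 8.8.2 as fallbacks).

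Confirm the item mapping against the scoring key, and say how the answer for subjects with no symptoms is classified. Record the departure from Protocol 3.2.4 in SAP section 10. The planned analyses of the other KCCQ subscores and the overall summary score stay as they are.

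The cost is about one sentence of analysis text and a small change to one set of exploratory tables. No new data are needed.

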8.10.4. Renal Endpoint Analyses

The following endpoints will be evaluated in the Renal Evaluable Population, unless otherwise specified.

8.10.4.1. Renal Response

In addition to the secondary endpoint for the Renal Evaluable Population, renal best response will be determined for different time intervals, such as through 3, 6, and 9 months of treatment. Best response at each of these time intervals and response at each visit will be analyzed in the same manner described in Section 8.9.1.

8.10.4.2. Renal Biomarkers

Renal biomarkers (urine albumin/creatinine ratio, urinary neutrophil gelatinase-associated lipocalin [NGAL] and urinary retinol-binding protein [RBP]) results, change from baseline, and

percent change from baseline to all visits will be analyzed in the same manner described in Section 8.8.1. Renal biomarkers will be evaluated in the Renal Evaluable Population and repeated for the ITT Population.

8.10.4.3. Creatinine, Proteinuria, and eGFR

Creatinine, proteinuria (measured by 24-hour urine total protein excretion), and estimated glomerular filtration rate (eGFR) to all visits will be analyzed in the same manner described in Section 8.8.1. Creatinine, Proteinuria, and eGFR will be evaluated in the Renal Evaluable Population and repeated for the ITT Population.

Shifts in Chronic Kidney Stage from baseline to worst post-baseline value, last post-baseline value, best post-baseline value, and at each post-baseline visit will be provided by treatment group. Shifts in Chronic Kidney Stage will be evaluated in the Renal Evaluable Population and repeated for the ITT Population.

8.10.5. Peripheral Neuropathy Endpoint Analyses

The following endpoints will be evaluated in the Peripheral Neuropathy Evaluable Population.

8.10.5.1. NIS-LL Total and Component Scores

In addition to the secondary endpoint for the Peripheral Neuropathy Evaluable Population, the NIS-LL total scores at other visits and the 3 deficit component scores (sensory function, reflexes, muscle strength) to all visits will be analyzed in the same manner described in Section 8.9.2.

Peripheral neuropathy response and progression as defined in [Coelho 2012 \(Appendix 2\)](#), are those with an increase from baseline in NIS-LL total score of <2 points and those with an increase from baseline in NIS-LL of ≥ 2 points, respectively. Response at each visit will be analyzed in the same manner described in Section 8.7 for the primary efficacy endpoint. Peripheral neuropathy response at each visit will be analyzed in the same manner described in Section 8.7.

The rate of change (i.e. slopes) in the NIS-LL component scores and total score will be analyzed in the same manner described in Section 8.8.3.

8.10.5.2. VASPI

For the Peripheral Neuropathy Evaluable Population with painful neuropathy, defined as a baseline VASPI score > 0 , the change and percent change from baseline at in VASPI scores will be analyzed in the same manner described in Section 8.8.1.

8.10.6. Hepatic Endpoint Analyses

The following endpoints will be evaluated in the Hepatic Evaluable Population.

8.10.6.1. Hepatic Response

In addition to the secondary endpoint, for subjects in the Hepatic Evaluable Population, hepatic best response will be determined for different time intervals, such as through 3, 6, and 9 months of treatment. Hepatic best response at each of these time intervals and response at each visit will be analyzed in the same manner described in Section 8.9.3.

Alkaline phosphatase values, change from baseline, and percent change from baseline to all visits will be analyzed in the same manner described in Section 8.8.1.

8.10.7. Additional Time-to-Event Endpoints

8.10.7.1. Time to All-Cause Mortality (Overall Survival)

Overall survival, time to all-cause mortality, will be calculated in days as the date of death minus the date of first study drug infusion plus 1. Subjects will be censored at their last assessment known to be alive prior to LSLV.

NEOD001 will be compared to placebo using the log rank test stratified by the randomization stratification factors. Kaplan-Meier (KM) estimates of the distribution of the time-to-event will be tabulated and graphed by treatment group. The tabulation will include the KM estimate of the medians, 25th and 75th quartiles, and corresponding 95% CIs, if estimable. The tabular and graphical summaries will include the at-risk counts for every visit. The number and percent of subjects censored and with events will be presented. The hazard ratio and 95% CI will be determined based on a Cox regression model stratified by randomization strata to estimate the magnitude of the effect.

In addition, the frequency of deaths in NEOD001 and placebo will be analyzed in the same manner described in Section 8.7 for the primary efficacy endpoint.

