3.7 Definition of End of Study

The study will end when the last subject completes 12 months of study treatment and the 30-day safety follow-up period (i.e., EOS Visit). Subjects who complete the study and meet the eligibility criteria will be considered for entry into a separate open-label extension study, during which subjects will receive active treatment and may receive concurrent chemotherapy.

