4.3 Early Treatment Discontinuation

If the subject discontinues study drug prior to the EOS Visit, they should return for an ETD Visit 30 (\pm 5) days after their final administration of study drug as per [Section 6.2](#). If a subject fails to return for the scheduled visit, a documented effort must be made to determine the reason. If the subject cannot be reached by telephone after 2 attempts, a certified letter will be sent to the subject (or the subject's legally authorized representative, if appropriate) requesting contact with the Investigator. This information will be recorded in the study records.

If the subject discontinues study drug prior to the EOS, but is willing to continue to participate in study visits, the subject should have an ETD Visit 30 (\pm 5) days after his/her final administration of study drug (per [Section 6.2](#)) and then have assessments monthly, through Month 12 per [Appendix 13](#). The subject will not have an EOS Visit. The most important visit is the Month 12-Day 1 Visit, so if a subject is unwilling to continue monthly visits, every effort should be made for the subject to return to the clinic and complete the Month 12-Day 1 Visit on schedule. All visits after the ETD Visit should occur on schedule, that is, at the time when their visit would have occurred had they remained on study drug. Following the Month 12-Day 1 Visit, subjects will be followed for vital status per [Section 6.4](#).

Reasons for early discontinuation from study drug treatment may include, but are not limited to:

- Hematologic progression and initiation of chemotherapy is required; chemotherapy regimen should be documented on the appropriate electronic case report form (eCRF).
- Need for organ transplant or major surgery.
- A suspected NEOD001-related immunologic reaction – collect additional serum samples, if possible, during the period following the treatment stoppage to allow for the determination of the persistence of anti-NEOD001 antibodies. At a minimum, samples should be collected at the ETD Visit and 3 months after the ETD Visit, if the subject agrees to return to the clinic.
- Occurrence of an AE or clinically significant laboratory abnormality that, in the opinion of the Investigator, warrants the subject's permanent discontinuation from study drug treatment; the Medical Monitor should be notified as soon as possible of any discontinuation of study drug due to an AE.

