6.4 Vital Status Follow-Up Phone Call

For randomized subjects who received at least 1 dose of study drug, conduct vital status telephone call approximately 3 months after last visit and approximately every 3 months thereafter or until subject enrolls in a separate open-label study, death, or for up to 5 years.

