2.3.4.7. Additional Time-to-Event Endpoints

- Time to All-Cause Mortality (Overall Survival): Any after the first infusion of study drug (i.e. study day 1) through the study's last subject last visit (LSLV). Time (months) to event will be calculated as: (date of death - the date of first study drug infusion + 1) / 30.4375. Subjects will be censored at their last assessment known to be alive prior to LSLV.
- Progression free survival: Time (days) to event will be calculated as the earliest of event dates (cardiac disease progression or death) minus the date of first infusion of study drug plus 1.

- Duration of Cardiac Response: Time (days) to event will be calculated as the earliest date of disease progression subsequent to the first response minus the date of first response plus 1. Subjects never achieving response are excluded.
- Time to derived organ progression for each organ (cardiac, renal) separately
- Time to cardiac or renal progression
- Time to first organ response for each organ (cardiac, renal) separately
- Time to cardiac or renal response

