4.3. Partial Dates and Unknown Times

If only a partial date is available and is required for calculation, the following standards will be applied:

- Birth Date
 - For missing day only – Day will be imputed as the middle of the month (i.e., 15).
 - For missing day and month – Day and month will be imputed as the middle of the year (i.e., 15 June).
- Death Date
 - The last date that each subject was known to be alive will be identified as the greatest date associated with the subject's completed assessments, including telephone contacts at which the subject was confirmed to be alive.
 - For missing day only – Day will be imputed as the first day of the month (i.e., 1) with the following exception: if the partial date falls in the same month as the last known alive date, then the partial date will be imputed to equal the last known alive date.
 - For missing day and month – Day and month will be imputed as the first day of the year (i.e., 1 January) with the following exception: if the partial date falls in the same year as the last known alive date, then the partial date will be imputed to equal the last known alive date.
- Diagnosis Date
 - For missing day only – Day will be imputed as the first day of the month (i.e., 1).
 - For missing day and month – Day and month will be imputed as the first day of the year (i.e., 1 January).
- Start Dates (e.g., event date, adverse event [AE] onset date, or start date of medication)
 - For missing start day only – Day will be imputed as the first day of the month (i.e., 1) with the following exception: if the partial date falls in the same month and year as the date being used in the calculation (e.g., first infusion date, informed consent date), then the partial date will be imputed to equal the date being used for the calculation.
 - For missing start day and month – Day and month will be imputed as the first day of the year (i.e., 1 January) with the following exception: if the partial date falls in the same year as the date being used in the calculation (e.g., first infusion date, informed consent date), then the partial date will be imputed to equal the date being used for the calculation.
 - Imputed start dates must be prior to the stop date.
- Stop Dates (e.g., AE resolution date or stop date of medication)

- For missing stop day only – Day will be imputed as the last day of the month (i.e., 28, 29, 30, or 31).

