8.2. Handling of Dropouts or Missing Data

At any point in the study, if a subject is unwilling to continue monthly visits, every effort will be made for the subject to return to the clinic and complete the Month 12-Day 1 Visit on schedule. Subjects who discontinue study drug before the end of the study should have an ETD Visit 30 (± 5) days after their final administration of study drug, and if willing, have assessments monthly per Appendix 12. For randomized subjects who received any amount of study drug, vital status telephone calls will be conducted approximately 3 months after last visit and approximately every 3 months thereafter or until subject enrolls in a separate open-label study, death, or for up to 5 years.

For the SF-36v2, missing data conventions for partially completed questionnaires are specified in Section 2.3.4.3.1.

The following methods will be implemented to address missing data for relevant primary, key secondary, other secondary efficacy endpoint analyses, and select exploratory efficacy endpoints.

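### Overall survival runs to last subject last visit, but vital-status calls stop at extension entry, so the Kaplan-Meier curve after about month 11 over-represents early stoppers

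*SAP*

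**What the plan says.** - **OS rule.** SAP 2.3.4.7 counts deaths from first infusion to last subject last visit (LSLV). SAP 8.10.7.1 adds: "Subjects will be censored at their last assessment known to be alive prior to LSLV". The comparison is: "NEOD001 will be compared to placebo using the log rank test stratified by the randomization stratification factors". Kaplan-Meier estimates and a stratified Cox hazard ratio accompany it.
- **When calls stop.** Protocol 6.4 schedules vital-status calls about 3 months after the last visit and "approximately every 3 months thereafter or until subject enrolls in a separate open-label study, death, or for up to 5 years". SAP 8.2 and the schedule-of-assessments notes repeat this.
- **Who can enter the extension.** Protocol 3.7: "Subjects who complete the study and meet the eligibility criteria will be considered for entry into a separate open-label extension study".
- **Early stoppers.** Protocol 4.3: "Following the Month 12-Day 1 Visit, subjects will be followed for vital status".
- **Known-alive date.** The only definition is in the death-date rule of SAP 4.3. It uses completed assessments, "including telephone contacts at which the subject was confirmed to be alive". It mentions neither extension visits nor public sources.
- **Protocol 4.4.** Vital status is to be collected for every randomized subject given at least one dose, with a search of public sources. The close-out collection in the same section is limited to subjects who withdrew.

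SAP 8.10.7.1 has no rule for extension entry and no sensitivity analysis for this censoring. OS is outside the testing hierarchy in SAP 8.6.

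**The concern.** Kaplan-Meier, log-rank and Cox methods assume that a censored subject has the same later risk as those still followed. Here, leaving follow-up depends on completing the study and qualifying for the extension. Staying in follow-up is typical of subjects who stopped early or did not enter. Protocol 4.3 lists reasons for stopping such as hematologic progression needing chemotherapy, organ transplant and adverse events, so a worse prognosis among stoppers is plausible.

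The study ends at the last subject's EOS visit, so early enrollees can contribute OS time well beyond their own last visit. That late portion of the curve would describe mainly subjects who stopped or stayed out of the extension, yet it would be read as survival in the whole ITT population. If extension uptake or early stopping also differed by arm, the hazard ratio would move for reasons unrelated to mortality.

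**Working it through.** **Timing, from the documents.** Month 12 falls on day 11 × 28 = 308, and the EEOS target is 308 + 30 = 338. The EEOS window runs from 295 + 30 − 5 = 320 to 319 + 30 + 5 = 354. All match SAP Table 3. In months, 338 / 30.4375 = 11.1. The documents give no event count or power for OS, so there is no OS figure to reproduce.

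**Assumed inputs.** The documents give no death rate, stop rate, extension uptake or accrual length. Assume 15% early stoppers, a monthly death hazard of 0.03 in stoppers and 0.004 in completers, and uptake *u* of 70% or 95% among completers. Both arms are alike.

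**True survival.** S(t) = 0.15·exp(−0.03t) + 0.85·exp(−0.004t).
- S(11) = 0.921
- S(11.1) = 0.1075 + 0.8131 = 0.921
- S(22) = 0.0775 + 0.7784 = 0.856

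**Curve with entrants censored at Day 338.** After month 11.1 only stoppers and a fraction (1 − u) of completers remain, so

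KM(22) = S(11.1) × [0.0775 + (1 − u)·0.7784] / [0.1075 + (1 − u)·0.8131].

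- u = 70%: 0.921 × 0.311 / 0.351 = 0.815, about 4 points too low.
- u = 95%: 0.921 × 0.116 / 0.148 = 0.724, about 13 points too low.

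**Share of stoppers among those at risk at month 14.** Stoppers contribute 0.0986 and completers (1 − u)·0.8037.
- Everyone followed: 11%
- u = 70%: 29%
- u = 95%: 71%

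Simulation with 65 per arm gave the same values. A second run used 0.04 per month after stopping, 0.006 otherwise, 85% uptake and 18-month accrual. It gave 80.5% true against 69.6% planned at 24 months. Varying those hazards (0.02 to 0.04 against 0.004 to 0.006) and uptake (70% to 85%) gave errors of about 3 to 11 points. With equal hazards of 0.01 in stoppers and completers, the 22-month curve was 0.803 against 0.802, so there was no bias.

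**Test, with no true difference between arms** (65 per arm, unstratified log-rank, two-sided 0.05):

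| Pattern by arm | Rejection | HR |
|---|---|---|
| Equal stopping, equal uptake | 4.6% to 5.0% | about 1.00 to 1.01 |
| Uptake 90% vs 80% | 5.3% | 1.10 |
| Uptake 90% vs 70% | about 6% to 6.7% | 1.15 |
| Uptake 95% vs 50% | about 10% | 1.33 |
| Stopping 25% vs 15% (extra stoppers healthy), uptake 70% | 4.9% | 0.96 |
| Same, uptake 95% | 5.4% | 0.91 |

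In the uptake rows, an HR above 1 counts against the higher-uptake arm. In the stopping rows it favors the arm with more stopping. In both cases the arm that loses more of its good-prognosis subjects from follow-up looks worse. Cutting everyone near EEOS brought rejection in the uneven-uptake scenario back to 4.9% to 5.0%.

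**The case against.** The strongest counter-text is Protocol 4.4. It promises vital status for every dosed subject, makes no exception for extension entrants, and adds a public-source search. Protocol 6.4 ends only the telephone calls. A reader might infer that extension entrants are certainly lost to survival follow-up, and the documents do not establish that. What stands is that 4.4 sits in the early-termination section, its close-out collection covers withdrawn subjects, and the SAP never uses it to set dates for entrants. Partial use could even worsen matters. If a search added entrants' deaths while their alive time still ended at the last study visit, events would be counted without the matching survivor time.

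A reader might also infer that the OS test is biased as planned. That does not follow. With stopping and uptake equal by arm the log-rank test keeps its size, and a type I error near 10% needs a 45-point uptake gap. The study is double-blind, so uptake cannot follow known assignment, and nothing in the documents points to such a gap.

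Two further points are fair. The extension's eligibility criteria are not given in these documents, so a better prognosis among entrants is an inference. OS is also exploratory, with roughly 13 to 17 expected deaths under the inputs that assume a worse prognosis for stoppers, so any late comparison would be imprecise. These limit the severity but do not supply the missing rule.

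**Conclusion.** The concern holds for the late survival curve. As written, the OS rule and the call schedule together retain early stoppers and non-entrants after about Day 338 while extension entrants drop out. If those retained have a worse prognosis, the Kaplan-Meier estimate at 22 to 24 months is about 3 to 13 points too low. That range rests wholly on assumed hazards, stop rates and uptake. Survival to about month 11 is unaffected.

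For the arm comparison the concern is conditional: the hazard ratio and test are distorted only if stopping or extension uptake differs by arm, and modest differences move the type I error little. Severity is low to moderate, because OS is exploratory and outside the testing hierarchy.

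**What to change.** In SAP 2.3.4.7 and 8.10.7.1, state one follow-up rule for all dosed subjects, choosing one of these as the main analysis and the other as a sensitivity analysis:

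1. Censor everyone at the earlier of last known alive and Day 354, the end of the EEOS window.
2. Take both deaths and known-alive dates for extension entrants from the same sources (collection under Protocol 4.4 and the extension study) through one common cutoff. Extend the known-alive definition in SAP 4.3 to match.

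The cost is SAP wording, plus a data merge for the second option. Under the first, deaths after Day 354 leave that analysis. A small imbalance also remains, since an entrant last seen at Day 338 is censored up to 16 days (354 − 338) before others. Under the second, later follow-up includes time when former placebo subjects receive active treatment in the extension, and the report should say so.
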